2.0 Study Objectives

The primary aim of this study is to determine if GAE will reduce the severity of pain as well as global disability (resulting from the combination of pain, stiffness and difficulty performing daily activities) caused by knee OA compared with placebo. The secondary aim is to determine if GAE can result in the decreased necessity for ongoing conservative OA therapies such as medication therapy and joint injections.

3 Study Design

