3.2 Primary Study Endpoints

1. Overall efficacy of treatment as determined by a minimal clinically significant reduction in global Western Ontario and McMaster University

Osteoarthritis Index (WOMAC) questionnaire scoring of 16% at 1 and 6 month follow-up.

2. Minimal clinically important decrease of 15% on the pain VAS at 1 or 6 months follow-up.

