7.2 Effectiveness Assessments

Technical success will be defined as devascularization of hypervascular synovium at the affected knee. This will be determined during the procedure. Clinical success will be defined as a 16% reduction of the baseline global WOMAC score at 1 or 6 month follow-up (primary outcome) and a 15% reduction of the baseline pain VAS score at 6 or 1 month follow-up (primary outcome).

8 Statistical Plan

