8.2 Statistical Methods

The primary study endpoints, WOMAC and VAS scores, will be collected at baseline, 1 month follow-up, 3 month follow-up, and 6 month follow-up. Mean WOMAC and VAS scores will be reported at baseline, 1 month follow-up, 3 month follow-up, and 6 month follow-up, along with associated confidence intervals.

We will address the primary study endpoints by modeling each clinical outcome using random coefficient modeling. The clinical outcomes will be modeled as a linear function of time. We will allow a random intercept and slope that is dependent on treatment, so that each patient will have their own trajectory of pain over time. No additional covariates will be included in the model. We will employ a compound symmetric R-side covariance structure to account for dependencies arising from observations from the same patient. Random coefficient models are robust to missing values only require data to be MAR (and not the stronger assumption of MCAR), so that presence of missing values will not invalidate our conclusions.

We will compute predicted means, as well as the estimated difference in predicted means, at 6 months for both WOMAC and VAS; these will be derived from the population-averaged trajectories (i.e. fixed effects). We will test the H₀: $\mu_{sham, 6}$ months - $\mu_{GAE, 6 \text{ months}} = 0$ versus the one-sided alternative hypothesis H_a: $\mu_{sham, 6}$ months - $\mu_{GAE, 6 \text{ months}} > 0$ using a Wald test. Both primary study endpoints will be evaluated by considering significance of the p-value (p < 0.05) along with the percentage predicted mean difference with respect to the clinically relevant differences (16% for WOMAC and 15% for VAS). Both these factors will be taken in tandem as evidence to suggest GAE treatment efficacy. Primary endpoints will be assessed only at one time point, so that adjustment for multiple comparisons is not necessary since the evaluation of the primary endpoints for WOMAC and VAS each consists of only one statistical test. Non-significance of the p-value for this test will be considered inconclusive evidence against the null hypothesis. Variance components, including the intraclass correlation coefficient, will also be reported for each model. All analyses will use SAS version 9.4 (SAS Institute, Inc., Cary, NC).

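### The WOMAC primary endpoint is defined three ways and the VAS endpoint two; the stated reason for no multiplicity adjustment does not cover two primary endpoints, and no rule covers success on only one.

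*Combined protocol and SAP*

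**What the plan says.** Section 2.0 sets the aim to "determine if GAE will reduce the severity of pain as well as global disability".

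Section 3.2 defines the WOMAC endpoint as a reduction in global "questionnaire scoring of 16% at 1 and 6 month follow-up". It defines the VAS endpoint as "Minimal clinically important decrease of 15% on the pain VAS at 1 or 6 months follow-up".

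Section 7.2 defines clinical success as a "16% reduction of the baseline global WOMAC score at 1 or 6 month follow-up (primary outcome) and a 15% reduction", the second part being the VAS criterion: "15% reduction of the baseline pain VAS score at 6 or 1 month follow-up (primary outcome".

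Section 8.2 fits a random coefficient model to each outcome. It tests the sham-minus-GAE difference in predicted means at 6 months with a one-sided Wald test at p < 0.05. The p-value is considered along with the percentage predicted mean difference, set against 16% for WOMAC and 15% for VAS: "Both these factors will be taken in tandem as evidence to suggest GAE treatment efficacy". On multiplicity it says: "Primary endpoints will be assessed only at one time point, so that adjustment for multiple comparisons is not necessary", adding that each endpoint involves a single test. On a negative result: "Non-significance of the p-value for this test will be considered inconclusive evidence against the null hypothesis".

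Section 8.1 gives power per endpoint, at least 69.1% (WOMAC) and 51.7% (VAS). It gives none for the two together.

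**The concern.** There are three linked gaps.

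- **Which quantity is primary.** Success at both visits, success at either visit and a between-arm mean difference at one visit are different endpoints. Results could differ according to which section is followed.
- **The reason for no adjustment.** One time point and one test per endpoint answers multiplicity over visits and within an endpoint. It does not answer multiplicity across WOMAC and VAS. Its premise also fails against 3.2 and 7.2, which name two visits.
- **The conclusion for the trial.** Section 8.2 says how to read each test but not how two results become one statement about efficacy. If one endpoint succeeds and the other does not, the report could call the trial positive or inconclusive with equal support from the plan.

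**Working it through.** **Step 1. The definitions side by side.**

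| Endpoint | 3.2 | 7.2 | 8.2 |
|---|---|---|---|
| WOMAC | 16% reduction, months 1 and 6 | 16% reduction from baseline, month 1 or 6 | between-arm difference in predicted means, month 6 |
| VAS | 15% decrease, month 1 or 6 | 15% reduction from baseline, month 6 or 1 | between-arm difference in predicted means, month 6 |

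WOMAC has three versions. VAS has two, since 3.2 and 7.2 name the same visits.

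**Step 2. Reproduce 8.1.** Inputs: N = 21 at 2:1 (3.1), so 14 vs 7; WOMAC mean 12.2, SD 1.9; VAS mean 72, SD 13.3 (8.1). Two-sample t-test, 19 df, one-sided 0.05, critical value 1.729, SE factor sqrt(1/14 + 1/7) = 0.4629.

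- WOMAC: d = 0.16 × 12.2 / 1.9 = 1.027; noncentrality 1.027 / 0.4629 = 2.219; power 68.9% (69.1% with d rounded to 1.03).
- VAS: d = 0.15 × 72 / 13.3 = 0.812; noncentrality 0.812 / 0.4629 = 1.754; power 51.9% (51.7% with d rounded to 0.81).

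The stated figures reproduce. So 8.1 takes the percentages of the baseline mean and spends the full 0.05 on each endpoint.

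**Step 3. Error if either endpoint suffices, p-values alone.** Error = 0.05 + 0.05 − P(both significant under the null). The documents give no WOMAC–VAS correlation, so 0 to 0.9 is assumed. Bivariate normal: 0.10 − 0.0025 = 9.75% at 0; 0.10 − 0.0122 = 8.8% at 0.5; 0.10 − 0.0319 = 6.8% at 0.9.

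**Step 4. Effect of requiring 16%/15%.** At the planning SDs, p < 0.05 needs an observed difference of 1.729 × 0.4629 × 1.9 = 1.52, or 12.5% of 12.2, for WOMAC. For VAS it needs 1.729 × 0.4629 × 13.3 = 10.65, or 14.8% of 72. The percentage is therefore the tighter bar. Simulation then gives an either-endpoint error of 4.7% to 3.6%. This depends on the SDs: if they are 25% larger it is roughly 8% to 6%.

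**Step 5. Power if both are required, and the chance of a split result.** On p-values alone, joint power comes from a bivariate normal with marginal powers 0.691 and 0.517, and P(exactly one) = 0.691 + 0.517 − 2 × joint. At correlation 0 that is 1.208 − 2 × 0.357 = 0.494. The rows with the percentage are simulated with true effects equal to the thresholds. Per-endpoint power is then about 50% (WOMAC) and 47% (VAS), because an observed difference exceeds its own true value only about half the time.

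| Quantity | Correlation 0 | 0.5 | 0.9 |
|---|---|---|---|
| Either suffices, error, p-values only | 9.75% | 8.8% | 6.8% |
| Either suffices, error, 16%/15% also required | 4.7% | 4.4% | 3.6% |
| Both required, power, p-values only | 36% | 43% | 50% |
| Both required, power, 16%/15% also required | 23% | 31% | 41% |
| Exactly one succeeds, p-values only | 49% | 35% | 20% |
| Exactly one succeeds, 16%/15% also required | 50% | 34% | 15% |

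At the planned effects, then, between about one trial in seven and one in two ends in the case the plan does not interpret.

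**The case against.** The strongest reply is that 8.2 fixes the analysis: one model, one contrast, one visit per endpoint. Sections 2.0 and 7.2 join pain and disability conjunctively, so both endpoints look required, and requiring both needs no adjustment. If two separate claims are intended instead, each is held at 5%. Much of this stands: the 6-month tests are not in doubt, and the documents do lean toward requiring both. But neither 2.0 nor 7.2 is a decision rule for the 8.2 tests, and 8.2 justifies the waiver on other grounds. The in-tandem sentence does not fill the gap. The two factors it pairs are the p-value and the percentage difference, not WOMAC and VAS.

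The figures are also open to challenge. Zero correlation is an extreme, since section 6.1 describes WOMAC as reflecting difficulty from pain. The t-test is the planning basis of 8.1, not the planned Wald test, and 8.1 calls its power a lower bound. Both points stand, which is why ranges are given.

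A reader might infer that the trial runs at close to 10% one-sided error. The documents do not support that: no sentence says either endpoint suffices, and the ordinary reading of 8.2 is that the percentage criterion must also be met. Nor do they support saying that VAS is defined three ways.

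**Conclusion.** The concern holds as a contradiction between sections and a wrong stated rationale; it should be fixed. WOMAC has three definitions and VAS two. The waiver rests on a premise that 3.2 and 7.2 contradict, and it does not address two primary endpoints each tested at one-sided 0.05. No rule covers success on one endpoint only.

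Inflated error is a conditional consequence, not an established one. It reaches 6.8% to 9.75% only if either endpoint supports a single overall claim and the percentage is not binding. If both endpoints are required, the decision not to adjust is right for a reason 8.2 does not give, and what is missing is the joint power. All sizes assume 14 vs 7 with no dropout, the 8.1 means and SDs, a t-test in place of the planned model and correlation between 0 and 0.9; the power figures also take true effects equal to the 16%/15% thresholds.

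The base of the percentage is a smaller matter of wording. Sections 7.2 and 8.1 both point to baseline, and 8.2 need only say so.

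**What to change.** 1. Reconcile 3.2, 7.2 and 8.2 to one definition and one time point per endpoint. The month 6 between-arm difference is what 8.2 already tests. In choosing, note that sham subjects without improvement may cross over after month 1 (3.1, 5.2, 6.5). How their later data enter a month 6 contrast is a separate question.
2. Replace the waiver sentence with a success rule that keeps the criterion 8.2 already states. For example: *Efficacy is concluded only if, for both WOMAC and VAS, the 6-month difference is significant at one-sided 0.05 and is at least 16% (WOMAC) or 15% (VAS) of the baseline mean; because both endpoints are required, no multiplicity adjustment is needed.* If the percentage is not meant to be required, say so explicitly.
3. In 8.1, report joint power for the chosen rule only, with the assumed correlation. On the present basis, for correlation 0 to 0.9, that is about 23% to 41% with the percentage criterion (about 50% and 47% per endpoint), or about 36% to 50% on p-values alone (69.1% and 51.7% per endpoint).

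The cost is wording in four sections, changed before outcomes are compared by arm. It needs no new visits, data or subjects. The downside is a less favourable stated power.

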3.3 Secondary Study Endpoints

1. Reduction of previously initiated OA medical therapy (e.g. NSAIDs) at 12 months follow-up.

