4.3 Inclusion Criteria

- 1. Moderate to severe knee pain (VAS > 50 mm), and
- 2. Pain refractory to at least 3 months* of conservative therapies (antiinflammatory drugs, or physical therapy, or muscle strengthening, or intraarticular injections), and
- 3. Kellgren-Lawrence grade 1, 2 or 3 on radiograph of the knee.
- 4. Age > 40 years.

*3 months was chosen because this time interval is thought adequate for knee pain to be considered refractory to conservative care.

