5.4 Prior and Concomitant Therapy

The subjects will be required to have been on conservative therapy for OA for at least three months prior to undergoing GAE. They will be allowed to continue previously initiated therapies throughout the study period, but if new or escalated therapies are required past the post-operative period (14 days), the treatment will be considered a failure.

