6.1 Screening Visit (Visit 1)

Potential enrollees will first be identified and will undergo a standard knee OA work-up to include history and physical exam with emphasis on specific site of knee tenderness. The Western Ontario and McMaster University Osteoarthritis Index (WOMAC) questionnaire will be administered to assess difficulty as a result of pain, stiffness and overall decreased function secondary to knee pain in the past week.

Current pain will also be assessed using a visual analog scale (VAS). A knee radiograph will be obtained and evaluated using the Kellgren-Lawrence grading scale. A baseline knee MRI will also be acquired to evaluate for concomitant pathology as part of routine orthopedic evaluation. If the patient previously had an MRI for clinical care that can be obtained from his/her medical record and used for the purposes of this study.

If a patient qualifies to be a subject in the study based on the inclusion and exclusion criteria listed in section 4.3 and 4.4, the local study coordinator, investigator or designee will provide the candidate with a copy of the approved informed consent. Written informed consent will be obtained if appropriate. If the patient wishes to take more time to review the study before enrolling, he/she may complete the consent process at the beginning of the next visit, prior to the study GAE procedure. Those candidates who are disqualified from study entry will be logged into the Screening Log with a reason for no study entry. A copy of the consent will be provided to the subject and the original filed in the study files.

Patients will be randomized at this point according to the schema created prior to the commencement of the study.

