6.14 Visit 8a, 8b, or 12c-12 month follow-up for all subjects

Subjects will be seen in clinic or contacted by phone or by teleconference per, the subject's preference, 180 +/- 10 days following GAE. The WOMAC questionnaire and VAS pain score will be completed and subjects will be evaluated for possible adverse events. Subjects will also provide an update about the necessity/frequency of pre-established conservative therapies. If an AE is suspected based on change in pain scores or functionality, an appropriate work-up will be performed which may include MRI.

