We will identify extreme primary endpoint values by computing studentized residuals and then conduct sensitivity analyses by deleting these outliers from the analysis datasets. We will repeat the above statistical tests and use results of the sensitivity analyses to corroborate conclusions reached in the primary analyses.

We will address the secondary study endpoint of reduction of OA by comparing frequency of OA medical therapy between the sham group, the crossover group, and the GAE group at 12 months. We will employ a chi-squared test to test the H_0 : frequency of OA medical therapy is equal for between the sham group, the crossover group, and the GAE group versus the one-sided alternative hypothesis. A p-value of < 0.05 will be taken as evidence to suggest that the frequency of OA medical between the groups. Non-significance of the p-value for this test will be considered inconclusive evidence against the null hypothesis.

Reduction in AE will be evaluated with a multilevel logistic regression model. The outcome of adverse events will be regressed on treatment status. We will employ a compound symmetric R-side covariance structure to account for dependencies arising from observations from the same patient. The H_0 : frequency of AE is equal for between the sham group and the GAE group will be assessed versus the two-sided alternative hypothesis with a statistical test of the treatment

parameter different than 0, with a p-value of < 0.05 taken as evidence to suggest that the frequency of OA medical therapy is not equal between the groups. Non-significance of the p-value for this test will be considered inconclusive evidence against the null hypothesis.

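### The secondary endpoint is a reduction in OA medication, but the planned test compares only 12-month frequency, with no baseline reference, across groups partly formed after randomisation

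*Combined protocol and SAP*

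**What the plan says.** Section 2.0 gives the secondary aim as to "determine if GAE can result in the decreased necessity for ongoing conservative OA therapies such as medication therapy and joint injections". Section 3.3 turns this into one endpoint: "Reduction of previously initiated OA medical therapy (e.g. NSAIDs) at 12 months follow-up". Both describe a change from an earlier level.

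Section 8.2 says the endpoint will be addressed by "comparing frequency of OA medical therapy between the sham group, the crossover group, and the GAE group at 12 months". The null hypothesis of the chi-squared test is that "frequency of OA medical therapy is equal for between the sham group, the crossover group, and the GAE group versus the one-sided alternative hypothesis". For this endpoint the documents give no baseline value, change score, threshold for a reduction or baseline adjustment. Frequency is not defined.

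On data collection, section 6.14 says of the 12-month visit: "Subjects will also provide an update about the necessity/frequency of pre-established conservative therapies". The 1-, 3- and 6-month visits have the same item. The screening visit in section 6.1 lists a "standard knee OA work-up to include history and physical exam with emphasis on specific site of knee tenderness", then WOMAC, VAS, radiograph and MRI. It does not name therapy frequency as an item.

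On entry, section 5.4 states: "The subjects will be required to have been on conservative therapy for OA for at least three months prior to undergoing GAE". Section 4.3 accepts any one of "antiinflammatory drugs, or physical therapy, or muscle strengthening, or intraarticular injections".

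Sections 5.2 and 6.5 create the crossover group. Sham subjects without symptom improvement at 1 month are unblinded and offered embolization (Arm C).

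**The concern.** A 12-month frequency and a reduction since baseline are different quantities. Two groups can have the same use at 12 months after very different changes, or differ at 12 months only because they differed at the start. A significant result from the planned test would not show that therapy had been reduced, and a null result would not show that it had not.

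In a trial of randomised arms, an outcome-only comparison is usually defensible because baseline is balanced in expectation. Two features weaken that here. The arms are very small, and two of the three groups compared (sham and crossover) are defined by what happened in the first month. The subjects who stay in the sham group are those who improved by 1 month or who declined the second procedure. They are probably better placed than the sham arm as randomised, and the crossover group probably worse.

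At stake is the only secondary endpoint, which carries the trial's claim about less need for ongoing therapy. The primary endpoints are not affected.

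**Working it through.** The plan gives no power, rate or expected count for this endpoint, so there is no figure of its own to reproduce. The power figures in section 8.1 (69.1% and 51.7%) concern WOMAC and VAS.

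**1. Endpoint against test.** Section 3.3 needs two values per subject, the earlier therapy level and the 12-month level. The test in section 8.2 uses only the 12-month value. The primary outcomes, by contrast, are collected at baseline and modelled over time.

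**2. Can baseline medication differ between subjects?** Yes. Section 5.4 requires conservative therapy, but under section 4.3 physical therapy or muscle strengthening alone qualifies. A subject may therefore enter on no OA medication.

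**3. How likely is a chance imbalance?** Section 3.1 gives 21 subjects at 2:1, so 21 × 2/3 = 14 GAE and 21 × 1/3 = 7 sham. Let X ~ Bin(14, p) and Y ~ Bin(7, p) be baseline users, with p assumed. The gap is X/14 − Y/7 = (X − 2Y)/14. It is at least 0.20 in size when |X − 2Y| ≥ 2.8, that is, at least 3. The standard deviation of the gap is √[p(1 − p)(1/14 + 1/7)]. Summing the exact binomial probabilities gives:

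- p = 0.50: SD 0.231, probability 44.5%
- p = 0.70: SD 0.212, probability 40.3%
- p = 0.85: SD 0.165, probability 27.1%

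**4. Can the two questions give different answers?** The counts below are assumed, and both examples use two arms. Neither is the result of the planned three-group test.

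*Different baselines.* Suppose baseline users are 14/14 (GAE) and 3/7 (sham), a deliberately large gap. At 12 months users are 6/14 and 3/7, and nobody starts anew.

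- 12-month use: 42.9% v 42.9%, chi-squared p = 1.00.
- Reduction: (14 − 6)/14 = 8/14 v (3 − 3)/7 = 0/7. Chi-squared = 21 × (8 × 7 − 6 × 0)² / (14 × 7 × 8 × 13) = 6.46, p = 0.011. Two-sided Fisher p = 0.018.
- Four of these sham subjects had no medication to reduce. Among baseline users only, the comparison is 8/14 v 0/3. Here P(0 of 3) = C(14,8)/C(17,8) = 3003/24310 = 0.124, and the less likely opposite extreme is 2002/24310 = 0.082, so two-sided Fisher p = 0.21.

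The last line shows that the definition must say how subjects with no baseline medication count.

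*Partial reductions, if frequency means any use v none.* Suppose 11/14 v 2/7 cut their therapy but only 3/14 v 0/7 stop. One-sided Fisher p is 0.041 for reduced and 0.27 for stopped. The contrast is fragile: 10/14 v 2/7 reduced gives 0.08, and 11/14 v 3/7 gives 0.13. Other counts reverse it: 10/14 v 4/7 reduced gives 0.43, while 8/14 v 0/7 stopped gives 0.015.

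**5. Group sizes.** Sham and crossover together hold 7 subjects. With two outcome categories, the smaller expected count in a group of n is at most n/2, so at most 3.5 in either group. The usual minimum of 5 for the chi-squared approximation cannot be met there. A three-group chi-squared test also has no single direction, so the one-sided alternative is undefined.

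**The case against.** The strongest reply is that randomisation balances baseline in expectation, so 12-month use compared between arms estimates a treatment effect without a baseline term. That is correct as a general statement. It would largely answer the point if the comparison were between the two arms as randomised, leaving only chance imbalance and the wording of the endpoint. Section 8.2 does not plan that comparison.

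A second reply is that follow-up visits ask about pre-established therapies, which implies an earlier record, and that a history is taken at Visit 1. This stands as far as data collection goes. A reader might infer that baseline therapy is not collected at all. The documents do not support that, because the case report form is not among them and the flow chart in section 6.15 is not readable. The reply does not put baseline into the test.

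A third reply concerns the meaning of frequency. A reader might infer that a subject who cuts use sharply without stopping is necessarily counted as unchanged. That follows only if frequency means any use v none. The follow-up wording may equally mean how often, and a test on ordered or grouped frequencies would pick up part of such a cut. What is established is that the variable is undefined.

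A reader might also infer that all subjects start on medication, so that most of the signal is discarded. Section 5.4 speaks of conservative therapy, not medication, and no rates are given from which to judge how much is lost. If everyone did start on medication, the any-use reading would have no baseline imbalance, and non-use at 12 months would itself be a reduction.

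**Conclusion.** The point holds. Followed exactly, section 8.2 would not measure the endpoint in section 3.3. It omits the baseline level, leaves reduction and frequency undefined, and compares groups that are partly defined by 1-month response.

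The mismatch and the post-randomisation split rest on the text alone. The 27% to 45% probability of a 20-point baseline gap rests on the 14:7 split and on assumed prevalences of 85% to 50%. The loss of partial reductions is conditional on the any-use reading. The p-values are illustrations with assumed counts. They show that the two questions can give different answers, not that the planned test would miss a real effect or by how much.

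This concerns a secondary endpoint with no power claim, so it does not threaten the trial's main conclusion. It should still be corrected, because it is the only secondary endpoint and a claim of reduced therapy could not rest on the test as planned.

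**What to change.** - **Baseline.** Confirm that the Visit 1 form records type and frequency of each OA medication, and add the field if it does not. State whether joint injections, named in section 2.0, count as medical therapy.
- **Definition.** Define reduction per subject against the Visit 1 level. Say how subjects with no baseline medication count, and how escalation counts, given that section 5.4 already classes it as treatment failure.
- **Comparison.** Compare the two arms as randomised, either with an exact test on reduced v not reduced or with a baseline-adjusted analysis of 12-month frequency. The second keeps more information on the size of change. State whether the test is one- or two-sided. Report crossover subjects descriptively.
- **Clock.** State from which procedure the 12 months run for crossover subjects. Section 6.14 labels the visit 12 months but gives a window of 180 +/- 10 days after GAE. These must be reconciled.

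The cost is SAP wording and possibly one form field. If the trial is under way without structured baseline data, the level would have to be taken from the Visit 1 history, and that should be reported.

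The downside is dilution. Sham subjects who crossed over will have received GAE by 12 months. If k of 7 cross over and then respond like the GAE arm, and response does not depend on who crosses over, only (7 − k)/7 of the true difference remains. For example, k = 4 leaves 3/7 = 43%. The as-randomised contrast should be interpreted as a comparison of immediate GAE with sham followed by optional GAE.

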5.2 Method for Assigning Subject to Treatment Groups

Subjects who meet all criteria for study entry and have signed written informed consent will be randomized in a 2:1 allocation of treatment (geniculate artery embolization) versus placebo (angiogram). Patients will be blinded to the study procedure. Each patient will be told at the time of recruitment that they may be

randomly assigned to GAE or sham. If after 1 month if they have not had symptom improvement, their assigned procedure would be revealed only if they had undergone a sham procedure. They will then be allowed to proceed with embolization in Arm C if they elect to proceed. This second procedure should be shorter than a complete angiogram and embolization, as the detailed angiogram will not need to be repeated. See table 1 (study schema). A 2:1 ratio was selected so that patients would be more likely to enroll in the study.

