6.5 Visit 5a and 5b - 1 Month Follow-Up

Subjects will be seen in clinic or contacted by phone or by teleconference, per the subject's preference, 30 +/- 7 days following GAE or sham procedure. The WOMAC questionnaire and VAS pain score will be completed and subjects will be evaluated for possible adverse events. An MRI of the treated knee will be acquired for those subjects who underwent GAE*. Subjects will also provide an update about the necessity/frequency of pre-established conservative therapies.

For those subjects who do not report improvement in symptoms or worsening, and are in the placebo arm, they will be unblinded and offered to undergo the geniculate artery embolization (Arm C) and then followed at similar follow-up intervals to 12 months (24 hours, 2 weeks, 1 month, 3 months, 6 months, and 12 months).

*MRI is only scheduled at one month in order to evaluate for non-target ischemic injury. These types of injuries will become apparent as early as 24 hours after embolization. Infarcted tissue will still be detectable at one month. Based on our experience with embolization in other areas, it is thought extremely unlikely that new ischemic injury related to the procedure will develop after the one-month follow-up. Additionally, findings that would be detected on later scans may be unrelated to the procedure and confound the data.

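### The 12-month OA-medication test is called one-sided but has no direction, and it splits the randomised sham arm after randomisation, so p < 0.05 does not by itself isolate a GAE effect

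*Combined protocol and SAP*

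**What the plan says.** Section 2.0 gives the secondary aim: to "determine if GAE can result in the decreased necessity for ongoing conservative OA therapies". Section 3.3 lists one secondary endpoint: "Reduction of previously initiated OA medical therapy (e.g. NSAIDs) at 12 months follow-up".

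Section 8.2 analyses it with a chi-squared test at 12 months. The null hypothesis is that "frequency of OA medical therapy is equal for between the sham group, the crossover group, and the GAE group versus the one-sided alternative hypothesis". No direction, ordering of groups or pairwise contrast follows. A p-value below 0.05 is to be "taken as evidence to suggest that the frequency of OA medical between the groups", a sentence that stops before it says what has been shown. The adverse-event paragraph of 8.2, which states a two-sided alternative, ends with wording that looks meant for the medication endpoint: "the frequency of OA medical therapy is not equal between the groups".

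Randomisation is to two arms, 2:1 in 21 subjects (3.1, 5.2). The crossover group forms later. Section 6.5 says: "For those subjects who do not report improvement in symptoms or worsening, and are in the placebo arm, they will be unblinded". Section 5.2 adds: "They will then be allowed to proceed with embolization in Arm C if they elect to proceed". The sham group at 12 months is what remains of that arm. The GAE arm is not divided by month-1 response.

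**The concern.** There are two faults, and neither needs an assumed rate.

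**Direction.** A Pearson chi-squared statistic across three groups adds squared deviations, so it treats a benefit and a harm of the same size alike. The primary tests in 8.2 have a written direction (sham mean minus GAE mean above zero). This test has none. If the unfinished sentence is completed like its neighbour in the adverse-event paragraph, the alternative is simply inequality, which contradicts one-sided.

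**Grouping.** The hypothesis of three equal groups can be false only because sham patients who improved by month 1 differ at 12 months from those who did not. That is a contrast within one randomised arm, whereas the aim in 2.0 is about the effect of GAE. The plan gives no as-randomised comparison for this endpoint.

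At stake is the interpretation of the trial's only listed secondary endpoint: a significant p-value could be reported as an effect of GAE on medication use when the randomised arms do not differ.

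**Working it through.** **Inputs.** N = 21 at 2:1 gives 14 GAE and 7 sham (3.1). The three groups and p < 0.05 come from 8.2. Assumptions, because the documents are silent: therapy is coded yes/no (reduced or not), which gives 2 df and a critical value of 5.991; the number crossing over; and all response rates.

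**The plan's own figures.** No power is stated for this endpoint. The primary figures in 8.1 confirm the design inputs. A two-sample t-test with 14 v 7, one-sided 0.05, gives 68.9% for WOMAC (difference 0.16 × 12.2 = 1.952, SD 1.9; stated 69.1%) and 51.9% for VAS (difference 0.15 × 72 = 10.8, SD 13.3; stated 51.7%).

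**Formula.** Chi-squared = Σ nᵢ(pᵢ − p)² / [p(1 − p)], where pᵢ is the proportion in group i and p the pooled proportion.

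**1. Direction.** Split the sham arm 4 crossed, 3 not.
- GAE 4/14, crossover 4/4, remaining sham 3/3: p = 11/21 = 0.5238 and p(1 − p) = 0.2494. Numerator 14 × (0.2857 − 0.5238)² + 7 × (1 − 0.5238)² = 0.794 + 1.587 = 2.381. Chi-squared = 2.381/0.2494 = 9.55, p = 0.0085.
- GAE 10/14, crossover 0/4, remaining sham 0/3: p = 10/21 = 0.4762, with the same p(1 − p). Numerator 14 × (0.7143 − 0.4762)² + 7 × 0.4762² = 2.381. Chi-squared is again 9.55, p = 0.0085.

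GAE is much worse in the first table and much better in the second. The test cannot tell them apart.

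**2. Grouping.** GAE 6/14, crossover 0/4, remaining sham 3/3: p = 9/21 = 0.4286 and p(1 − p) = 0.2449. The GAE term is 14 × (0.4286 − 0.4286)² = 0. The sham terms are 4 × 0.4286² + 3 × 0.5714² = 0.735 + 0.980 = 1.714. Chi-squared = 1.714/0.2449 = 7.00, p = 0.030. The randomised arms are 6/14 v 3/7, both 43% (Fisher p = 1.0). The whole statistic comes from within the sham arm.

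**3. How often this could happen.** Exact enumeration of three binomials (14, k crossed, 7 − k not; k = 1 to 6). There is no GAE effect, all non-improvers cross, and the GAE rate equals the sham arm's mixture.

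| Assumed rate of reduced medication, month-1 improvers v non-improvers | Rejection at nominal 5% |
|---|---|
| 55% v 45% | 3.1–4.6% |
| 60% v 30% | 3.5–9.1% |
| 70% v 20% | 4.8–19.9% |

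At 70% v 20%, GAE is behind the remaining sham patients in 65–97% of the rejections.

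**4. Power of an as-randomised test.** Assumed rates of 70% with GAE v 30% with sham; crossed patients respond like GAE patients, and crossover is unselected.

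| Crossed, of 7 | Fisher two-sided | Fisher one-sided | Planned test |
|---|---|---|---|
| 0 | 28.7% | 39.7% | 42.9% |
| 2 | 13.4% | 20.4% | 27.8% |
| 4 | 5.6% | 8.5% | 20.5% |

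The planned test has 1 df when nobody crosses.

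**The case against.** The plan compares frequencies by group, so a reader will see which group used less medication. Section 8.2 does not call p < 0.05 evidence of efficacy for this endpoint, and it treats non-significance as inconclusive. If nobody crosses, the test becomes the randomised 14 v 7 comparison. The table giving p = 0.030 is an illustration: even at 70% v 20% with a 4/3 split, its probability is only about 3%. The as-randomised test loses power.

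All of that is correct, and it limits the point. A reader might infer that the endpoint cannot inform the secondary aim at all. That goes too far: the observed frequencies can show direction, but the test does not supply it, and its p-value does not attribute the difference to GAE.

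A reader might also infer that the analysis is biased towards GAE or has an inflated error rate. The documents support neither. At 55% v 45% there is no inflation, the higher rates need a strong link between month-1 status and later medication, and at 70% v 20% most false rejections have GAE behind the remaining sham patients.

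The power advantage of the planned test once patients cross comes from a split that was not randomised, so it is not a reason to keep it. Comparing later frequency between randomised arms is a plausible way to measure reduction, so the difference in wording between 3.3 and 8.2 is minor.

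**Conclusion.** The point holds in this form: one-sided is undefined for the planned test, and p < 0.05 does not by itself isolate a GAE effect. Both conclusions follow from the text of 8.2, 5.2 and 6.5 without any assumed rate. The worked tables assume a yes/no outcome and a 4/3 split. The rejection rates (3.1–4.6% up to 4.8–19.9%) and the power figures rest on assumed response rates as well.

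The change should be made, but it concerns one secondary endpoint without a stated power in a 21-patient trial. Nothing here shows that the primary 6-month tests are affected or that they are safe. Section 8.2 does not say how data after crossover enter that model, and this point does not assess it.

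**What to change.** In 8.2:
- Make GAE v sham as randomised the only inferential comparison for this endpoint, by Fisher's exact test with an exact confidence interval. The numbers are nominally 14 v 7; 8.3 ties inclusion to 12-month data, so they may be smaller.
- State the direction if one-sided 0.05 is kept, or call the test two-sided. Either is coherent with two arms.
- State how therapy is coded, and complete the sentence on what p < 0.05 shows.
- Report the crossover and never-crossed sham groups descriptively only.
- Say that crossed patients have had GAE by 12 months, so the contrast is diluted and equal arms would not show absence of effect.
- As support, report the as-randomised comparison at month 1, limited to data collected before any crossover GAE. Section 6.5 already collects what is needed: "Subjects will also provide an update about the necessity/frequency of pre-established conservative therapies".

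The cost is SAP wording and power. With four of seven crossing, Fisher's test has 5.6% (two-sided) or 8.5% (one-sided) at 70% v 30%, so the estimate and interval should carry the weight. The month-1 comparison precedes the dilution but answers a shorter-term question.

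Separately, the visit timing must be reconciled. Section 6.14 is headed 12 months but gives the 180-day window of the 6-month visits (6.8, 6.13). Section 6.7 counts crossover GAE from visit 4, the 2-week call, although unblinding is at the 1-month visit.
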